Patients will be provided with background information about the study*, including the premise of the study, patient pathways, and what their participation would involve. The patient will have an opportunity to ask questions and a written WOLVERINE Study patient information sheet (PIS) will be provided as an adjunct to this conversation.

A record of the discussion with the patient will be kept in the patient's medical notes.

*The patient-facing documents will be available in the national language of each participating country.

PATIENT CONSENT

Informed consent within the WOLVERINE cohort study will be documented in REDCap.

Wolverine Protocol IRAS: 334321

^{**}Ideally, potential participants will be identified pre-operatively.

WOLVERINE is a non-interventional study; there are no clinical interventions additional to those received as part of routine clinical care. Only routinely collected, anonymised data will be collected by the clinician at baseline and 30-days.

However, at the 30, 60, 90 days and 6-month, one-year post-op follow-up time points, patient reported outcomes will be collected remotely via REDCap, thus consent is required for the collection and analysis of this data.

Patient consent is therefore specifically sought for the permission to collect the follow-up data via the remote monitoring system and to contact the patient at the 30, 60, 90 days and 6-month, one-year post-operative follow-up time points via email or text reminders. Participants will be contacted up to three times at each timepoint to request completion of the questionnaires. Reminders will be sent via an automated email reminder from the central team at the University of Birmingham. As part of the consent process, patients will be asked to provide their email address and mobile phone number.

Process for consent for follow-up

Consent will be obtained remotely via REDCap.

Once a patient is identified as eligible, their surgeon or another member of their direct clinical care team will discuss the study with them. They will be provided with the PIS to facilitate the discussion.

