The patient will be provided with a unique patient identification number by the person discussing the study with them (this is taken from the site-specific WOLVERINE REDCap LINK SHEET provided by the study office). This unique identifier will be recorded on the WOLVERINE PIS. Eligible patients will also be provided with a generic QR code. This QR code and unique identifier will be used by the potential participants to access the REDCap-WOLVERINE system and the consent form.

The potential participant will then be asked to access the online system at a time convenient to them, i.e. they do not need to access the system whilst in hospital. Upon access of the online REDCap system, they will be asked for consent for follow-up.

This unique REDCap ID will be the only identifier used to identify the patient in any correspondence between the coordinating centre and the participating site.

*Participating sites may download the consent form as a PDF if required for the WOLVERINE Site File.

STUDY FOLLOW-UP

Follow-Up Time points

After the baseline visit, there are no further study-specific visits. All study-specific follow-up is conducted via remote reporting.

There are 5 follow-up time points: 30-, 60- AND 90-days post-surgery; 6 months and one year post-surgery.

Short-term follow-up: 30-days post-surgery

- Clinician reported:
 - o Conducted without the need for patient attendance.
 - No specific follow-up visit is mandated for participants.
 - The 30-day post-surgical outcomes form is undertaken by the clinical team, with routinely collected information from patient notes or electronic records, or other routinely collected data sources.
- Patient reported
 - Data is collected remotely from the participant via the WOLVERINE online REDCap system
 - Bluebelle wound healing questionnaire, EQ-5D5L, SF-12, the Patient reported Wound Recovery PROM QoL and the ESCP Incisional Hernia PROM.

Longer-term follow-up

At the 60-days, 90-days, 6-month and 1 year post-operative timepoints, data is collected remotely from the patient only. The following questionnaires will be requested:

- The EQ-5D5L and the SF-12 at each of the 4 timepoints.
- Bluebell wound healing questionnaire at 30 days.
- Patient reported Wound Recovery PROM at 60 days and 90 days.
- ESCP incisional hernia PROM at 3-, 6- and 12-months.
- HerQles questionnaire at 1 year

^{**}There is no clinical team involvement beyond 30-days post-surgery.

COHORT STUDY SCHEDULE OF EVENTS

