SAMPLE SIZE - COHORT STUDY

Based on feasibility, we assume that each hospital provides data on at least 10 consecutive eligible patients over a 4-week recruitment period.

PROJECTED RECRUITMENT

Based on previous studies, 1,000 patients are expected to enter the cohort study.

ANALYSIS PLAN

Analysis will be performed after data has been cleaned and locked. The analysis will descriptively summarize the types of wound closure and SSI prevention measures, and the primary and secondary clinical outcomes in the audit and cohort study populations.

In the cohort study, there is potential for patients to be lost to follow-up, resulting in a variable duration of time over which outcomes may be ascertained for each patient. If follow-up varies systematically by site or wound closure techniques, this could introduce bias into the analyses of outcomes. To address this, each investigator/site should establish a plan to record the frequency, dates, and method/setting (e.g., phone, in-person) of contacts with patients when measuring outcomes over the course of the follow-up period. For example, if an investigator/research staff's last contact with a patient is completed 6 months into follow-up, but no subsequent contacts are successfully accomplished with the patient, the patient will be considered as lost to follow-up (censored) on the date of the last successful contact and will be considered as contributing 6 months of person-time to the analysis.

Upon completion of the cohort study data collection, we will examine the distribution of follow-up for all patients to determine its completeness and plan an appropriate course of action regarding statistical analysis, such as the use of complete case analysis with inverse probability of censoring weights or survival analysis methods (e.g., Cox proportional hazards models), if required. We will detail the specifics of these analyses in a statistical analysis plan after examining the empirical distributions of the data in a manner that is agnostic to the relationship between outcomes and treatment/wound closure exposure group.

Selected relevant risk scores for development of surgical site infections, surgical site occurrences, and abdominal wound dehiscence will be compared against the data collected in this study.

Planned additional analyses

A full statistical analysis plan will be published prior to study completion. Example of the analyses will include -

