The IAC will also provide a further layer of overall supervision for the study and ensure that it is being conducted in accordance with the protocol, the principles of Good Clinical Practice and other relevant regulations. The IAC will meet face-to-face or via teleconferencing at the start of the project and every twelve months thereafter.

The specific tasks of the IAC include:

- To agree the study protocol and any protocol amendments.
- To resolve problems brought to it by the WOLVERINE study management group.
- To provide advice to the investigators on all aspects of the study.

ETHICS & CONSENT

Patients will not undergo any additional investigations for the purposes of this study. Clinical follow-up will be limited to review of health records up to a maximum of 30 days postoperatively.

Additional patient contact (telephone, in-person, by email or by application) will take place between 30 days postoperatively and one year postoperatively to collect patient data.

The cohort study will be conducted and reported according to STROBE (Strengthening the Reporting of Observations studies in Epidemiology) guidelines.

DATA MANAGEMENT

Principal investigators at each participating site are responsible for obtaining necessary local approvals. Data will be collected in two phases. During the index admission, pre-operative and intra-operative data will be collected. Local Principal Investigators will establish pathways in their hospitals to ensure robust data collection; for example, pre-operative data could be collected in the morning prior to surgery, with intra-operative data fields completed in theatre immediately following completion of the procedure. Alternatively, all index data including patient registration could be collected in theatre, or in the post-operative ward.

Collection of post-discharge follow-up data

Patients who are discharged from hospital early may be more likely to develop a surgical site infection out of hospital and often fail to be noted or registered. A review of the participating patients' clinic visit notes and letters will therefore be mandatory for all participating hospitals. All

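### The censoring date rests on site-recorded patient contacts that the described follow-up does not produce after day 30, and it is not tied to the last hernia assessment

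*Protocol*

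**What the plan says.** The Analysis Plan (Protocol, Statistical Considerations) warns that follow-up differing by site or closure technique could bias the outcome analyses. As a safeguard it says that "each investigator/site should establish a plan to record the frequency, dates, and method/setting (e.g., phone, in-person) of contacts with patients". Its example is a patient last reached by an investigator or research staff at 6 months: "the patient will be considered as lost to follow-up (censored) on the date of the last successful contact", with 6 months of person-time.

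Other sections of the protocol describe follow-up differently:

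- Study Follow-Up: "All study-specific follow-up is conducted via remote reporting". From 60 days on, at the "post-operative timepoints, data is collected remotely from the patient only". A note adds: "There is no clinical team involvement beyond 30-days post-surgery".
- Patient Consent: up to three requests per time point, and "Reminders will be sent via an automated email reminder from the central team at the University of Birmingham".
- Ethics & Consent: "Additional patient contact (telephone, in-person, by email or by application) will take place" between 30 days and one year.
- Patient Withdrawal: failure to reach the patient is a reason for withdrawal. Withdrawn patients' data are kept for baseline analyses and reports.

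The hernia instrument is listed under Longer-term follow-up as "ESCP incisional hernia PROM at 3-, 6- and 12-months", and the Schedule of Events agrees. The short-term list in Study Follow-Up also places it at 30 days. Neither place has it at 60 days. Mortality is a listed outcome only to 30 days, and health-record review stops at 30 days.

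**The concern.** A censoring rule needs a date that the study records, and the patient must have been assessed for the outcome up to that date. This rule is doubtful on both counts. It gives the recording duty to sites that otherwise have no part after day 30. It also dates follow-up by contact, whereas hernia is seen only when its own questionnaire is completed.

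At stake is the denominator of any rate or time-based analysis of the long-term outcomes, and who counts as having a known one-year status. If sites interpret the rule differently, follow-up time will vary by site for reasons unrelated to patients, which is what the Analysis Plan sets out to prevent. An analysis plan written later can choose a model. It cannot supply contact dates or deaths that nobody was asked to record.

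**Working it through.** The protocol has no figure to reproduce here, so the check is a comparison of sections followed by worked cases.

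**Who contacts the patient after day 30**

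| Protocol section | Who | How |
|---|---|---|
| Analysis Plan | each investigator or site | phone and in person, as examples |
| Study Follow-Up | patient only; no clinical team | remote, REDCap |
| Patient Consent | central team | automated email; consent also covers text |
| Safety Considerations | no site contact described; the sole study-specific activity is gathering patient reports | REDCap |
| Data Handling, Data Management | surgeon-level data at baseline and 30 days, patient-level data from 30 days to one year | REDCap |
| Ethics & Consent | not stated | telephone, in person, email, application |

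Under Study Follow-Up, the 6-month staff contact in the Analysis Plan's example would not occur. Under Ethics & Consent it could.

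**What the rule gives for one patient**

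*Case 1: all questionnaires completed to 12 months.* If only site contacts count, none falls after day 30, and the 30-day clinical form is itself completed without attendance. Follow-up is at most 30 days for a patient observed for a year.

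*Case 2: 30- and 60-day questionnaires completed, then silence.*
- Site contacts only: at most 30 days.
- Any contact, including a questionnaire: 60 days.
- Last hernia questionnaire: 30 days if the short-term list stands; none (0 days) if the Schedule of Events stands.
- Patient Withdrawal: kept for baseline analyses, with nothing said about outcome analyses.

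The any-contact reading credits 60 − 30 = 30 days, or 60 − 0 = 60 days, as hernia-free without a hernia assessment.

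*Case 3: everything completed at 90 days, only the quality-of-life forms returned at 6 months, nothing later (assuming forms can be returned separately).* Last contact is at 6 months and last hernia assessment at 3 months, so 6 − 3 = 3 months are credited without assessment.

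How often these cases would arise is unknown, because the protocol states no dropout or response rate.

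**Deaths after day 30**

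With no source described, a later death cannot be told apart from non-response. The illustration below assumes constant, independent hazards over one year. Let h be the one-year hernia risk estimated with deaths censored, and d the one-year mortality. With a = −ln(1 − h) and b = −ln(1 − d), the cumulative incidence with death as a competing event is a/(a + b) × [1 − exp(−(a + b))].

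Example with h = 10% and d = 5%: a = 0.1054 and b = 0.0513, giving 0.6726 × 0.1450 = 9.75%.

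| Assumed mortality d | 2% | 5% | 10% | 20% |
|---|---|---|---|---|
| h = 10% | 9.9% | 9.75% | 9.5% | 9.0% |
| h = 20% | 19.8% | 19.5% | 19.0% | 18.0% |

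The overstatement is 0.1 to 1.0 percentage points at h = 10% and 0.2 to 2.0 at h = 20%. It is an upper-side illustration, since deaths in the first 30 days are recorded and need not be censored.

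**The case against.** **Phone and in-person are only examples, so a completed questionnaire could count as a contact.** This is a fair reading and probably the workable one. The sentence still gives the recording to sites, and nothing defines a successful contact.

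**The sentence goes on to limit the contacts to those at which outcomes are measured.** This stands in part. A reader might infer that any logged call earns hernia-free time and put a percentage on the diluted rate. The text does not support that: it does not describe contacts without outcome measurement, and it gives no rates from which to calculate. But the qualifier does not say which outcome. A 60-day contact measures quality of life and, if the wound is unhealed, wound recovery, but not hernia.

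**Ethics & Consent agrees with the Analysis Plan.** It does on means of contact, so it would be wrong to call the design uniformly remote-only. The protocol contradicts itself, and the sections need reconciling.

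**A reader might infer that the protocol commits to Cox models with exact event times for hernia.** It does not. Cox is a conditional example beside complete-case analysis with inverse probability of censoring weights. No outcome is named, and the specifics are left to the statistical analysis plan. Late failure is defined by hernia at one year, so a binary analysis is open. The fixed grid also matters little. In simulations with 1,000 patients, 300 runs per scenario, complete follow-up and a true hazard ratio of 0.50, one-year hernia risks of 10%, 20% and 40% gave 0.492, 0.509 and 0.499 with exact times. Times recorded only at 3, 6 and 12 months gave 0.492, 0.509 and 0.500 (Efron ties); Breslow ties gave at most 0.522. Missed or late questionnaires were not tested. The choice of model is no part of this point.

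**The protocol never says that deaths will be censored, and handling of competing events may be left to the analysis plan.** Both are true. What remains is that no data source for later deaths is described. The study also calls itself hypothesis-generating, which limits the consequences.

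**Conclusion.** The point holds as an internal contradiction in a stated rule. The Analysis Plan bases censoring and person-time on site-recorded contacts. Study Follow-Up and Patient Consent describe follow-up that produces none after day 30, Ethics & Consent says otherwise, and Patient Withdrawal classifies the same patients differently. Even on the most generous reading, the end of follow-up is not tied to the last assessment of the outcome being analysed.

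The effect on hernia rates cannot be sized from the protocol. The worked cases show one patient's follow-up moving by 30 days to several months with the reading chosen, but not how many patients are affected. The late-death gap is real and secondary: under the assumptions shown it is small at low mortality and reaches 1 to 2 percentage points at 20%. The protocol states no one-year mortality, so no claim is made about any particular subgroup. The rule should be corrected before the follow-up data are analysed.

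**What to change.** 1. Reconcile Patient Consent, Study Follow-Up, Patient Withdrawal, the Analysis Plan and Ethics & Consent on who contacts patients after day 30, by what means, and whether an unreachable patient is withdrawn or censored.
2. Remove the site contact log. Define the end of follow-up separately for each patient-reported outcome as the REDCap completion date of the last questionnaire that measures it. For hernia this is the last completed ESCP incisional hernia PROM. Settle at the same time whether that instrument is given at 30 days.
3. State that deaths after day 30 have no described source. Then either record deaths that become known to the study, with dates, or report one-year hernia incidence with the explicit limitation that death and non-response cannot be separated.

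Items 1 and 2 are wording changes. They remove a site duty and use dates that REDCap should already hold, at the price of a separate end date per outcome in the analysis files. Recording known deaths needs one field and will be incomplete, so the limitation should be stated in either case. Actively searching records for later deaths would need an amendment to the 30-day limit on record review and a new site task, and is not required to resolve this point.
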